8.5.5.1 Adverse events

AEs will be coded using the Medical Dictionary for Regulatory Activities (MedDRA). All AEs will be summarized by treatment group. The number and percentages of patients who experienced at least 1 AE will be summarized by system organ class and preferred term. AEs will also be summarized by relationship to the study medication and by severity. Deaths, SAEs, and AEs leading to study discontinuation will be tabulated and presented in data listings. Patient level data listings of all AEs will be presented.

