3.9 Discontinuation of investigational product

Patients may be discontinued from the study medication in the following situations:

- Patient decision. The patient is at any time free to discontinue treatment, without prejudice to further treatment.
- Patient experiences an AE that, in the investigator's opinion, necessitates discontinuation from study medication.
- The investigator decides that the patient should discontinue study medication. If this decision is made because of a serious adverse event (SAE) or a clinically significant abnormal laboratory value, appropriate measures are to be taken. The Sponsor or its designee is to be alerted immediately. Refer to Section 6.4, Reporting of SAEs.
- Severe non-compliance with the study protocol.
- Calculated creatinine clearance <45 mL/min confirmed by repeat testing or a decrease in renal function that would preclude continued treatment with metformin according to local guidance.
- Loss of glucose control. If any patient experiences a loss of glucose control, in addition to study medication, the investigator should initiate rescue therapy and the patient may continue study participation. The

investigator should follow local prescribing information for the rescue therapy and may discuss appropriate rescue therapy with the AstraZeneca Medical Monitor if needed. Patients must first complete the Rescue visit procedures before receiving open-label rescue therapy. Rescued patients with central laboratory HbA1c values $>8.0\%$ despite a maximum tolerated dose of rescue therapy for 12 weeks will be discontinued from the study and referred for additional anti-hyperglycemic therapy (see Section 4.2).

- Patients with a central laboratory ALT and/or AST $>3x$ ULN will be scheduled for a follow-up visit within 3 days following the receipt of the result (see Appendix C, “Algorithm on Management of Sustained Elevated Liver Safety Abnormalities”). Patients should be discontinued from study medication if the initial and repeat laboratory tests meet any of the following criteria:
 - ALT and/or AST are $>3x$ ULN **and** TB $>2x$ ULN.
 - ALT and/or AST are $>5x$ ULN for ≥ 14 consecutive days, at any time after initial confirmatory results.
 - ALT and /or AST are $>8x$ ULN.

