3.9.1 Procedures for discontinuation of a patient from investigational product

If deemed necessary by the investigator, study medication can be stopped temporarily and then re-started after discussion with the medical monitor. These situations will be handled on a case by case basis and all decisions will be documented in the patient’s study file.

At any time, patients are free to discontinue study medication or withdraw from the study (ie, study medication and assessments – see Section 3.10), without prejudice to further treatment. A patient that decides to discontinue study medication will always be asked about the reason(s) and the presence of any AEs. AEs will be followed up (see Section 6); patient diaries and all study medications should be returned by the patient.

Patients who discontinue permanently from the study medication will have an Early Termination Visit equivalent to the Week 28 assessments at the time of study medication discontinuation (see Section 4.2.2). Discontinued patients will then be contacted via telephone according to the visit schedule in the Study Plan (Table 1 and Table 2), ie, during the time windows during which the scheduled clinic visits would have been conducted. At these contacts, the following data will be collected and entered onto the clinical database:

- Concomitant medication
- AEs

Discontinued patients should return to the study site and complete assessments required for Visit 12 (Week 28), Visit 15 (Week 52), and Visit 19 (Week 104) as appropriate and outlined in the Study Plan ([Table 1](#) and [Table 2](#)). These patients will also be contacted via telephone according to the visit schedule in the Study Plan ([Table 1](#) and [Table 2](#)).

Discontinued patients should also return to the study site to complete the Follow-up visit (Visit 20) 10 weeks after the Visit 19 (Week 104) assessments.

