3.10 Criteria for withdrawal

Every reasonable effort should be made to conduct all protocol-required procedures to complete the study. Patients may be removed from the study for the following reasons:

1. Screen failures: see Section [3.10.1](#).
2. Withdrawal by patient: see Section [3.10.2](#).
3. Adverse Event: Patient experiences an AE that, in the investigator's opinion, necessitates withdrawal from the study.
4. Investigator Decision: Investigator feels it is in the patient's best interest to terminate participation for reasons other than an AE.
5. Protocol Violation: Patient is noncompliant with protocol procedures, becomes pregnant, violates study entry criteria, or starts an exclusionary concomitant medication.
6. Lost to Follow-Up: Patient fails to return for study visits and cannot be reached with reasonable, repeated attempts.
7. Study Terminated by Sponsor: The Sponsor discontinues the study protocol.
8. Administrative Reasons: The FDA or other regulatory authority discontinues the study protocol or the clinical study site discontinues participation.

Any withdrawal must be fully documented in the patient's source records and recorded on the Disposition page of the electronic case report form (eCRF). The documentation must include the reason for the withdrawal and details of any sequelae (followed until symptoms resolve or improve, as appropriate). Withdrawals due to an AE must be documented on the eCRF.

If a patient is withdrawn from the study, they must complete the procedures outlined in Section 3.9.1, Procedures for discontinuation of a patient from investigational product.

When a patient is lost to follow-up (ie, fails to return for study visits), a reasonable effort (eg, a documented minimum of 2 calls and a certified letter) will be made to contact the patient to determine why the patient failed to return and to attempt to schedule the Early Termination Visit (refer to Table 1 and Table 2).

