6.3.3 Variables

The following variables will be collect for each AE;

- AE (verbatim)

- The date and time when the AE started and stopped
- Maximum intensity
- Whether the AE is serious or not
- Investigator causality rating against the IP (yes or no)
- Action taken with regard to IP
- Outcome.

In addition, the following variables will be collected for SAEs:

- Date AE met criteria for serious AE
- Date investigator became aware of serious AE
- AE is serious due to
- Date of hospitalization
- Date of discharge
- Probable cause of death
- Date of death
- Autopsy performed
- Causality assessment in relation to study procedure(s)
- Description of AE.

The maximum intensity of an AE will be rated according to the following definition:

- Mild (awareness of sign or symptom, but easily tolerated)
- Moderate (discomfort sufficient to cause interference with normal activities)
- Severe (incapacitating, with inability to perform normal activities).

It is important to distinguish between serious and severe AEs. Severity is a measure of intensity whereas seriousness is defined by the criteria in Section 6.2. An AE of severe intensity need not necessarily be considered serious. For example, nausea that persists for several hours may be considered severe nausea, but not a SAE unless it meets the criteria shown in Section 6.2. On the other hand, a stroke that results in only a limited degree of

disability may be considered a mild stroke but would be a SAE when it satisfies the criteria shown in Section 6.2.

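### The adverse-event table in Section 8.5.5.1 is keyed to leaving the study, so read literally it can miss patients who stop study medication for an adverse event but remain in follow-up

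*Protocol*

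**What the plan says.** Section 8.5.5.1 (Adverse events) states: "Deaths, SAEs, and AEs leading to study discontinuation will be tabulated and presented in data listings". It also plans summaries of all AEs by system organ class and preferred term, by relationship and by severity, and adds that "Patient level data listings of all AEs will be presented". It names no table of AEs that led to stopping study medication.

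Elsewhere the protocol keeps two outcomes apart:

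- Section 3.9 lists as a reason to stop medication: "Patient experiences an AE that, in the investigator's opinion, necessitates discontinuation from study medication".
- Section 3.10 lists as a separate reason to leave the study: "Patient experiences an AE that, in the investigator's opinion, necessitates withdrawal from the study".
- Section 3.9.1 sets the two side by side: "patients are free to discontinue study medication or withdraw from the study".

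Patients who stop medication permanently are not lost to the trial. Section 3.9.1 says "Discontinued patients will then be contacted via telephone according to the visit schedule in the Study Plan", and AEs and concomitant medication are collected at those contacts. They are also asked back to the site at Weeks 28, 52 and 104 and for Visit 20.

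Section 6.3.3 records "Action taken with regard to IP" for each AE.

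**The concern.** The safety objective in Section 2.4 is to compare the safety and tolerability of the combination with that of each component. How often an AE leads a patient to give up the medication bears directly on that comparison. Under this protocol such a patient is meant to stay in the study. A table that counts only AEs leading to study discontinuation then records the event only if the patient also leaves, and the better the follow-up works, the fewer drug stops it shows.

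Section 6.3.6 makes the mismatch sharper. Deterioration in a protocol-mandated laboratory value or vital sign is to be reported as an AE only if it meets a seriousness criterion or is the reason for stopping the investigational product. Stopping the product can therefore be what turns a finding into an AE, yet Section 8.5.5.1 has no matching table. Section 1.3.1 warns that the combination may raise the risk of volume-related and renal events, and Section 3.9 includes a renal criterion among the reasons to stop medication. A non-serious event of that kind could be reported because medication was stopped and then fall outside the discontinuation table.

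**Working it through.** The protocol gives no figure for this point, so there is none to reproduce. The check is first a reading of the text and then an illustration of size.

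**Tracing three patients through the text**

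1. A patient has a non-serious AE, stops medication (Section 3.9) and is followed by telephone and site visits (Section 3.9.1). This patient has not discontinued the study. Read literally, Section 8.5.5.1 does not count the event in its discontinuation table.
2. A patient has a serious AE, stops medication and stays in follow-up. The event appears among the serious AEs but not as a discontinuation.
3. A patient has an AE and withdraws from the study (Section 3.10, item 3). The event is counted.

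The named table therefore captures the third case and leaves out the first two.

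**Possible size**

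Inputs:

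- Patients per arm: 660 randomized / 3 arms = 220 (Sections 3.3.1 and 8.2).
- r, the share of an arm that stops medication for an AE: not in the document; assumed 3%, 5% or 10%.
- f, the share of those patients who remain in the study: not in the document; taken from 0% to 100%.

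Formula: missed = 220 × r × f.

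| r (assumed) | AE-driven drug stops per arm | f = 0% | f = 25% | f = 50% | f = 75% | f = 100% |
|---|---|---|---|---|---|---|
| 3% | 6.6 | 0 | 1.65 | 3.3 | 4.95 | 6.6 |
| 5% | 11 | 0 | 2.75 | 5.5 | 8.25 | 11 |
| 10% | 22 | 0 | 5.5 | 11 | 16.5 | 22 |

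The incidence shown by the literal table is r × (1 − f). If f is the same in every arm, each incidence and each difference between arms shrinks by the factor (1 − f). If f differs between arms, the comparison itself is distorted. More than half of the drug stops are missed only when f exceeds 50%. Section 3.9.1 aims for high retention but puts no number on it.

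**The case against.** The strongest reply has three parts.

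*The list is not exclusive, and detail is left to the SAP.* Section 8.5.5.1 says what will be tabulated, not that nothing else will be, and Section 8.5.5 defers safety detail to the SAP, which is not at hand. This stands as far as it goes: a table of drug stops cannot be called missing from the plan, and a reader should not infer that the sponsor has excluded it. What remains is that the protocol itself names a category that does not match its own disposition scheme. A SAP that follows that sentence literally would inherit the mismatch.

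*The protocol uses the terms loosely, so study discontinuation may be meant to include drug stops.* This is plausible. Section 3.9.1 and footnote a of Table 2 use the word discontinued for patients who stopped medication and are still followed. Section 3.10 sends patients withdrawn from the study through the procedures of Section 3.9.1. The same liver criteria end study medication in Section 3.9 but end study participation in Appendix C. The argument shows that the defect may be one of wording and not a deliberate choice of analysis. It does not remove the problem, because two programmers could build different tables from the same sentence.

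*The information is not lost.* This is correct. The action taken with the product is recorded for each AE, and all AEs are summarized and listed. But a patient-level listing gives no incidence by arm, and the general AE summaries do not show which events ended treatment.

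**Conclusion.** The point holds as a minor one. Section 8.5.5.1 names a table keyed to study discontinuation. Read literally, it can miss AE-driven drug stops in patients who remain in follow-up. With 220 per arm and an assumed 5% drug-stop rate, between 0 and 11 patients per arm would be missed. Both the rate and the retention are assumptions.

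Three stronger readings are tempting and are not supported:

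- That the table misses most AE-driven drug stops. The document gives neither the rate of such stops nor the share of patients retained.
- That every patient who stops medication for an AE stays in the study. Section 3.10 allows withdrawal for an AE, and Section 3.10.2 allows withdrawal of consent.
- That AEs leading to treatment discontinuation are the trial's main tolerability measure. Section 2.4 names the incidence, duration and time course of AEs, laboratory tests, physical examination and vital signs.

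The table is descriptive. The primary analysis and its type I error are unaffected.

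**What to change.** In Section 8.5.5.1, replace the single category with two, each tabulated by arm:

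1. AEs leading to permanent discontinuation of study medication, derived from the action-taken field in Section 6.3.3.
2. AEs leading to withdrawal from the study, as a separate line.

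Section 3.9.1 also allows temporary stops, so the first category should say permanent. The protocol does not list the field's response options; confirm that they separate a permanent stop from an interruption.

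Use the two terms consistently in Sections 3.9, 3.9.1, 3.10 and 8.5.5.1 and in Appendix C. The liver criteria, which lead to stopping study medication in Section 3.9 and to leaving the study in Appendix C, must be reconciled by the sponsor.

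The cost is a revised sentence, one table and a terminology check. If the field distinguishes permanent stops, no new data are needed.

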8.5.5.2 Clinical laboratory

Clinical laboratory results (chemistry, hematology, urinalysis, etc.) will be summarized using descriptive statistics for each visit by treatment group. Observed values at each visit and changes from baseline to each post-baseline visit will be presented. Changes from baseline in high/low/normal findings for clinical laboratory parameters for which normal ranges apply will be summarized by treatment group using shift tables. All laboratory data will be provided in patient data listings.

8.5.5.3 Vital signs

Vital signs (BP, pulse) will be summarized by treatment group for each applicable visit. Observed and changes from baseline values will be summarized for each visit where appropriate.

8.5.5.4 Physical examinations

Shift from baseline in physical examination findings will be presented as appropriate.

8.5.5.5 Anti-exenatide antibodies

Antibody to exenatide data will be listed and summarized. A patient is said to have treatment-emergent antibodies to exenatide at a visit if the antibody test is positive after the first dose of randomized study medication following a negative or missing antibody measurement on or before the first dose of randomized study medication, or the titer is increased by at least 3 dilutions from a detectable measurement prior to the first dose of randomized study medication. The incidence of treatment-emergent antibodies to exenatide will be summarized by treatment, study visit, and individual titer, as appropriate. Subgroup analyses such as change in HbA1c and incidence of AEs by antibody response (or titer group) will be explored.

8.5.6 Subgroup analysis

The primary endpoint, change from baseline in HbA1c at Week 28, will be summarized descriptively for subgroups of interest (eg, age group, gender, ethnicity, race, country). Additional subgroup analysis may be performed as appropriate and details will be specified in the SAP.

8.5.7 Interim analysis

No formal interim analysis will be conducted.

The efficacy and safety analyses will be conducted when all the patients complete 28 weeks of treatment. The analyses for the entire 52-week treatment period will be performed when all the patients complete the Extension Period 1. Similar analyses for the entire 104-week treatment period will be performed when all the patients complete the Extension Period 2.

The trial will be on-going at the time of the analyses on data collected from the 28 weeks of treatment. The site and patients will remain blinded to the treatment assignment until the study completion and final database lock.

8.5.8 Sensitivity analysis

Sensitivity analyses will be performed on the primary endpoint (eg, ANCOVA). Details will be specified in the SAP.

9. STUDY AND DATA MANAGEMENT BY ASTRAZENECA

9.1 Training of study site personnel

Before the first patient is entered into the study, an AstraZeneca representative will review and discuss the requirements of the Clinical Study Protocol (CSP) and related documents with the investigational staff and also train them in any study specific procedures and the WBDC system utilized.

The Principal Investigator will ensure that appropriate training relevant to the study is given to all of these staff, and that any new information relevant to the performance of this study is forwarded to the staff involved.

The Principal Investigator will maintain a record of all individuals involved in the study (medical, nursing and other staff).

9.2 Monitoring of the study

During the study, an AstraZeneca representative will have regular contacts with the study site, including visits to:

- Provide information and support to the investigator(s)
- Confirm that facilities remain acceptable
- Confirm that the investigational team is adhering to the protocol, that data are being accurately and timely recorded in the CRFs, that biological samples are handled in accordance with the Laboratory Manual and that study medication accountability checks are being performed
- Perform source data verification (a comparison of the data in the CRFs with the patient's medical records at the hospital or practice, and other records relevant to the study) including verification of informed consent of participating patients. This will require direct access to all original records for each patient (eg, clinic charts)
- Ensure withdrawal of informed consent to the use of the patient's biological samples is reported and biological samples are identified and disposed of/destroyed accordingly, and the action is documented, and reported to the patient.

The AstraZeneca representative will be available between visits if the investigator(s) or other staff at the center needs information and advice about the study conduct.

9.2.1 Source data

Refer to the Clinical Study Agreement (CSA) for location of source data.

9.2.2 Study agreements

The Principal Investigator at each/the center should comply with all the terms, conditions, and obligations of the CSA, or equivalent, for this study. In the event of any inconsistency between this CSP and the CSA, the terms of CSP shall prevail with respect to the conduct of the study and the treatment of patients and in all other respects, not relating to study conduct or treatment of patients, the terms of the CSA shall prevail.

Agreements between AstraZeneca or representative and the Principal Investigator should be in place before any study-related procedures can take place, or patients are enrolled.

9.2.3 Archiving of study documents

The investigator follows the principles outlined in the CSA.

9.3 Study timetable and end of study

The end of the study is defined as 'the last visit of the last patient undergoing the study'.

The first patient is expected to be enrolled 3rd Quarter of 2014. The study is expected to complete 4th Quarter 2017

The study may be terminated at individual centers if the study procedures are not being performed according to GCP, or if recruitment is slow. AstraZeneca may also terminate the entire study prematurely if concerns for safety arise within this study or in any other study with EQW or dapagliflozin.

9.4 Data management by AstraZeneca or delegate

Data management will be performed by the CRO, according to the Data Management Plan. AEs and medical/surgical history will be classified according to the terminology of the latest version of the MedDRA. Medications will be classified according to the AstraZeneca Drug Dictionary (AZDD). Classification coding will be performed by the Medical Coding Team at the CRO.

Data entered in the electronic data capture (eDC) system will be immediately saved to a central database and changes tracked to provide an audit trail. When the Principal Investigator has signed the eCRF electronically as per eCRF instructions, then the patient's data will be locked

Electronic case report forms

The eCRF and the protocol are both confidential. The eCRF will be created by Quintiles and programmed into the eDC system. All study centers will need internet access to access the eCRFs and will only have access to data for patients at their own study centers. Data Management (DM) and other coordinator teams will have access to data at all study centers. All eCRFs are to be completed by an authorized member of the study center staff and reviewed and signed by the investigator. All entries, corrections, and alterations are to be made by the responsible investigator or an authorized member of the study center staff. All eCRFs are to be completed in a manner that ensures accurate interpretation of data. It is each investigator's responsibility to ensure that all discontinued orders or changes in the study or other medications entered on the patient's eCRF correspond to the entries on the patient's medical records.

The eCRFs for any patient leaving the study should be completed at the time study medication is terminated or a patient discontinues study participation for whatever reason. The eCRFs must accurately reflect data contained in the patient's records (eg, source).

Dataflow

After the data are entered into the eCRF by study center, auto-queries that are generated by the eDC system should be addressed by the study center. Data queries will be raised for inconsistent, impossible, or missing data. At the monitoring visit, the Study Monitor must perform the study data verification (SDV) of the required fields on completed forms, and if there are no open queries, freeze the form. DM will run manual consistency checks outside of the eDC system and will raise manual queries for study centers to address; if the form is frozen, DM will unfreeze it to allow study centers to amend data. The same process is to be followed by any other groups creating manual queries in the eDC system (eg, for SAE reconciliation). Once all data are entered, SDV complete on required fields, manual queries and electronic data reconciliation complete, and all queries closed, then the casebook can be signed. Once the casebook is signed, DM will then lock the casebook so that no amendments can be made.

Database lock

Once all patient casebooks are locked, the final data transfer can be sent to statistics. A database lock checklist will also be completed by DM and the programmer to confirm all applicable quality control checks were performed. When all data have been coded, validated, and locked, clean file will be declared. Any treatment revealing data may thereafter be added and the final database will be locked.

Coding

All AEs and Medical Histories recorded in the eCRF will be classified according to the terminology of the latest version of the MedDRA. Medications will be classified according to

the AZDD. The coding will occur outside of the eDC system and will be merged with the clinical datasets sent to statistics.

The data collected through third party sources will be obtained and reconciled against study data.

The data will be validated as defined in the Data Management Plan. Quality control procedures will be applied to each stage of data handling to ensure that all data are reliable and have been processed correctly. The Data Management Plan will also clarify the roles and responsibilities of the various functions and personnel involved in the data management process.

Serious Adverse Event (SAE) Reconciliation

Quintiles will perform SAE reconciliation between the Quintiles clinical study database and the safety data entry site clinical patient safety database.

Data associated with human biological samples

Data associated with biological samples will be transferred from laboratory(ies) internal or external to AstraZeneca.

